3. STUDY OBJECTIVES AND ENDPOINTS

The objectives and endpoints of the study shows below:

Objectives	Endpoints
Primary	
1. To compare change in HbA1c from baseline to 24 weeks between insulin analog mid mixture BID and basal insulin analog QD treatments	1. The change in HbA1c from baseline to 24 weeks
Secondary	
2. To compare change in HbA1c from baseline to 48 weeks between insulin analog mid mixture BID and basal insulin analog QD treatments	2. The change in HbA1c from baseline to 48 weeks
3. To compare the proportion of patients who achieve HbA1c <7% at 24 and 48 weeks between insulin analog mid mixture BID and basal insulin analog QD treatments	3. Proportion of patients who achieve HbA1c <7% at 24 and 48 weeks
4. To compare the change in venous FPG from baseline to 24 and 48 weeks between insulin analog mid mixture BID and basal insulin analog QD treatments	4. Venous FPG change from baseline at 24 and 48 weeks
5. To compare the change in FSBG-based FBG and PPG from baseline to 24 and 48 weeks between insulin analog mid mixture BID and basal insulin analog QD treatments	5.FSBG-based FBG, PPG change from baseline at 24 and 48 weeks
6. To compare the daily insulin dose at 24 and 48 weeks between insulin analog mid mixture BID and	6. Daily insulin dose at 24 and 48 weeks

basal insulin analog QD treatments	
7. To compare the change in body weight from baseline to 24 and 48 weeks between insulin analog mid mixture BID and basal insulin analog QD treatments	7. Body weight change from baseline at 24 and 48 weeks
8. To compare the severe, nocturnal and total hypoglycemia incidences and rates during the 24-week and 48-week treatment period between insulin analog mid mixture BID and basal insulin analog QD treatments	8. The severe, nocturnal and total hypoglycemia incidences and rates during the 24-week and 48-week treatment period

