7. HANDLING OF MISSING DATA AND OUTLIERS

7.1. Handling of Missing Efficacy Data

The baseline value for efficacy measurements, which include HbA1c, FPG, FSBG-based FBG, PPG, BG excursion, daily insulin, body weight, SEITQ score, will be defined as the last non-missing observation on or before the randomization visit. If no data are available, the baseline value will be treated as missing. The last records within each window (Appendix 1) will be used for analyses for Week 24/Week 48.

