8. GENERAL STATISTICAL CONSIDERATIONS

Additional exploratory analyses of data will be conducted, as deemed appropriate.

Given the nature of this pragmatic study, both efficacy and safety analyses will be performed on randomized patients. As sensitivity analyses, certain efficacy analyses may be repeated by censoring all efficacy data after patients changed the randomized treatment regimen.

All tests of treatment effects will be conducted at a 2-sided alpha level of 0.05, unless otherwise stated.

For continuous measures, summary statistics will include at least the number of patients with data, mean, SD, median, minimum, and maximum. For categorical measures, summary statistics will include at least the number of patients with data, frequency counts, and percentages. For comparisons based on analysis models, the differences will be reported using LS means, along with 95% CIs and p-value. Sometimes, comparison on the summary statistics may be performed and p-values be provided, and such p-values should be viewed as a descriptive measure only. Unless specified otherwise, a two-sample t-test will be used for continuous measurements and Fisher's exact test will be used for categorical measurements. Mean and median will be presented with one more decimal place than the precision of the data. Standard deviation will be presented with two more decimal places than the precision of the data. Minimum and maximum will be presented with the same precision as the original data.

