8.2.2. Secondary Analyses

Missing efficacy values which are HbA1c, FPG, FSBG-based FBG, PPG, BG excursion daily insulin, body weight, SEITQ score will do LOCF. Those missing values will be the last non-missing post-baseline observation up to date of missing values of measurement.

All secondary efficacy endpoints will be listed separately for each subject at each planned visit.

1. For change from baseline in HbA1c at Week 48, the analyses model will be similar to the primary analyses model, and the sensitivity analyses will also be performed.

Also, a mixed-model repeated measures (MMRM) model will be employed to analyze the HbA1c change from baseline at Week 24 and Week 48. This MMRM model will have all post-baseline HbA1c as responses, baseline HbA1c as a continuous covariate, treatment group, Visits (Week 24 or Visit 48), and treatment by visit interaction as fixed effects and patient as a random effect. An unstructured covariance structure will be used to model the correlation within subjects. In case of failure of convergence using unstructured covariance structure, the first-order autoregressive [AR(1)] covariance structure will be used. Missing data will be assumed to be missing at random and therefore maintained as missing. The difference between each of treatment will be assessed by the least-squares means (LSM) difference at Week 24 and Week 48 (alpha=0.05, 2-sided).

A plot of least-squares means for change from baseline by visit for each treatment will be used to display the results of this endpoint.

As sensitivity analyses, the endpoint analyses will be repeated by censoring all efficacy data after patients changed the randomized treatment regimen at Week 48, Ancova analyses for row data and LOCF data at Week 48 separately.

2. For change from baseline in venous FPG, FSBG-based FBG, PPG, BG excursion and bodyweight at Week 24 and Week 48, the analyses will be done similarly to the primary analyses model (ANCOVA for Week 24 and Week 48, and MMRM for Week 24 and Week 48), except for comparison will be based on the treatment contrast p-value from the corresponding analyses model. The sensitivity analyses will also be performed.

Plots of least-squares means for change from baseline by visit for each treatment will be used to display the results of endpoints.

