As sensitivity analyses, the endpoint analyses will be repeated by censoring all efficacy data after patients changed the randomized treatment regimen at Week 24 and Week 48, Ancova analyses for row data and LOCF data at Week 24 and Week 48 separately.

3. For percentages of patients reaching treatment goals (<7%) at Week 24 and Week 48, no missing data will be imputed. Count and percentages of patients reaching treatment goals will be summarized (when calculating percentages, the denominator will be the patients with non-missing HbA1c data at Week 24 or Week 48), and also be analyzed by a logistic regression model, with logit link function, treatment as fixed effect and baseline HbA1c as continuous covariate. Adjusted odds ratio, 95% CI and P-value will be presented. Related plot will be reported.

Plots of percentages of patients reaching treatment goals by visit for each treatment will be used to display the results of endpoints.

As sensitivity analyses, the endpoint analyses will be repeated by censoring all efficacy data after patients changed the randomized treatment regimen at Week 24 and Week 48, Ancova analyses for row data and LOCF data at Week 24 and Week 48 separately.

4. Same analyses strategy (refer to above 3) will be used for the composite endpoint of patients reaching treatment goals (<7%) and did not switch from or discontinue study treatment, and did not take rescue medication. Those patients should be without switching or discontinuing study insulin, and without using rescue therapy which will be determined by the investigator following usual standard of care between insulin analog mid mixture BID and basal insulin analog QD treatments.
5. Insulin dose at each visit will be descriptively summarized by treatment groups by total daily dose (IU and IU/kg). The descriptive statistics (n, mean, median, standard deviation, minimum, and maximum) and P-value of a two-sample t-test will be reported.
6. Time to insulin treatment change will be compared between treatment arms by a log rank test. Table and related plot will be reported. Patients who did not have any insulin treatment change up to Week 48 (or up to early discontinuation) will be considered as censored at Week 48 (or time of early discontinuation) with no event. Time to insulin treatment change: Defined as time to any of: insulin treatment

discontinuation, switch, intensification or reduction in frequency. ((date of event/censored - (date of first dose of study drug) + 1.)

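### Daily insulin dose is a secondary comparison but gets only an unadjusted t-test p-value; a baseline-adjusted difference with a confidence interval would be a modest, cheap improvement

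*SAP*

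**What the plan says.** Objective 6 in SAP section 3 is comparative: "To compare the daily insulin dose at 24 and 48 weeks between insulin analog mid mixture BID and" the basal arm. The analysis in SAP 8.2.2 item 5 begins "Insulin dose at each visit will be descriptively summarized by treatment groups by total daily dose (IU and IU/kg") and closes with descriptive statistics: "standard deviation, minimum, and maximum) and P-value of a two-sample t-test will be reported". No covariate, difference or confidence interval is listed. Protocol 10.3.3.2 plans the descriptive summary only, so the t-test is an addition made in the SAP.

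Two general rules in SAP section 8 bear on this. For tests run on summary tables: "comparison on the summary statistics may be performed and p-values be provided, and such p-values should be viewed as a descriptive measure only". For models: "For comparisons based on analysis models, the differences will be reported using LS means, along with 95% CIs and p-value". Because item 5 specifies no model, the second rule does not reach dose.

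Changes in HbA1c, FPG, finger-stick FBG and PPG, glucose excursion and body weight are all analysed by ANCOVA and MMRM (SAP 8.2.1 and 8.2.2 items 1 and 2). The logistic model for HbA1c below 7% also adjusts for baseline HbA1c (item 3).

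SAP 7.1 defines baselines as follows: "The baseline value for efficacy measurements, which include HbA1c, FPG, FSBG-based FBG, PPG, BG excursion, daily insulin, body weight, SEITQ score". Daily insulin is on that list. Footnote d to the protocol's Schedule of Activities explains that the Visit 1 entry is the dose the physician prescribed, and randomization takes place at the same visit.

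**The concern.** The dose difference tells a reader whether a difference in HbA1c, weight or hypoglycemia came with more insulin. A p-value alone does not give its size or precision, and item 5 promises nothing more. Titration is unrestricted (protocol 5.4 and 7.2.1), and eligibility sets no limit on weight and no upper limit on HbA1c (protocol 6.1 and 6.2). Dose in IU may therefore vary considerably between patients, and some of that variation may be predictable from values recorded before treatment. A t-test leaves the predictable part in the error term.

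There is also a trap for whoever programs the analysis. The other continuous glycemic and weight endpoints adjust for their own baseline, and SAP 7.1 names a baseline for daily insulin. Following that pattern would put the Visit 1 prescribed dose into the model. That value is set for the regimen the patient is about to start, so adjusting for it, or taking change from it, could remove part of the treatment difference being estimated.

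**Working it through.** **Inputs from the documents**
- 332 evaluable patients per arm, 1:1 allocation, 20% dropout (SAP section 5). Check: 332 / (1 − 0.20) = 415 per arm, 830 in total, as stated. These figures were set for HbA1c; the number with a dose value may differ.
- Two-sided alpha 0.05 (SAP section 8).
- No SD, power target or sample size is given for dose, and no correlation of dose with weight or HbA1c. There is thus no dose figure of the plan's own to reproduce.

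**Assumption**
- R² is the share of within-arm dose variance explained by baseline HbA1c and weight together. I take 0.02 to 0.25.

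**Step 1: unadjusted precision.** In units of the unknown within-arm SD of dose, the 95% half-width is 1.96 × √(2/332) = 0.1521.

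**Step 2: gain from adjustment.** The adjusted half-width is the unadjusted one times √(1 − R²). The equivalent sample size per arm is 332 / (1 − R²).

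| R² | √(1 − R²) | CI narrower by | Half-width (SD units) | Equivalent n per arm |
|---|---|---|---|---|
| 0.02 | 0.990 | 1.0% | 0.1506 | 339 |
| 0.05 | 0.975 | 2.5% | 0.1483 | 349 |
| 0.10 | 0.949 | 5.1% | 0.1443 | 369 |
| 0.20 | 0.894 | 10.6% | 0.1361 | 415 |
| 0.25 | 0.866 | 13.4% | 0.1317 | 443 |

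The percentage narrowing does not depend on the number of patients.

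**Step 3: price of two covariates.** Error degrees of freedom fall from 662 to 660. The width factor is √(662/660) times a ratio of t quantiles very close to 1, or 1.0015. Adjustment breaks even when (1 − R²) × 1.0015² = 1, that is, at R² of about 0.003. Net of this cost the range is 1 − 0.9899 × 1.0015 = 0.9% to 1 − 0.8660 × 1.0015 = 13.3%.

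**Step 4: IU against IU/kg.** As an illustration on assumed inputs, let dose in IU be weight times an IU/kg dose that is independent of weight, with coefficients of variation CVw and CVu. Weight then explains R² = CVw² / [(1 + CVw²)(1 + CVu²) − 1] of the variance in IU.
- CVw = 0.15, CVu = 0.60: 0.0225 / (1.0225 × 1.36 − 1) = 0.0225 / 0.3906 = 0.058, CI about 3% narrower.
- CVw = 0.20, CVu = 0.30: 0.04 / (1.04 × 1.09 − 1) = 0.04 / 0.1336 = 0.299, CI about 16% narrower.

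The second case lies slightly above the range in Step 2 and is a favourable one. Under the same assumption weight explains nothing on the IU/kg scale, where only baseline HbA1c could help.

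**Step 5: availability of the covariates.** Weight is scheduled at Visit 1. An HbA1c value within 12 weeks of entry is an inclusion criterion (protocol 6.1), so every eligible patient should have one. SAP 7.1 does allow a missing baseline, and such a patient would drop out of the ANCOVA but stay in the t-test.

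**The case against.** The strongest reply is that nothing here is wrong. Under randomization the two-sample t-test is valid. It is the SAP's default for continuous measures and is also used for ITSQ scores and for SEITQ change at Week 24. The ANCOVA endpoints adjust for their own baseline, and dose has no pre-insulin baseline. Dose is planned as a descriptive summary, and the p-value is descriptive under section 8, so no formal conclusion rests on it. All of that stands.

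Three further limits also stand. IU/kg already scales for weight. The documents give no correlation, so the claim that weight and HbA1c determine insulin requirement would be an outside premise, and the gain may be close to nil. Baseline HbA1c may be up to 12 weeks old, and follow-up dose is a single day's dose, or the last one taken if insulin was stopped; both could weaken any association.

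A reader might infer that the planned test is biased, or that the plan will report an interval that is too wide. The documents support neither: randomization protects the test, and item 5 lists no interval at all.

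What remains is that an objective worded as a comparison receives no estimate of the difference. An unadjusted mean difference with a confidence interval would fill that gap. ANCOVA fills it too, at almost no cost, and brings dose under the SAP's own reporting rule for models.

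**Conclusion.** The point holds as an optional refinement. SAP 8.2.2 item 5 meets a comparative secondary objective with a valid but unadjusted and descriptive p-value, and lists no difference or interval. Adjusting for covariates already collected would narrow the 95% confidence interval by about 1% to 13% for an assumed R² of 0.02 to 0.25, mainly on the IU scale. The lower end is as consistent with the documents as the upper end. Adjustment is not strictly free, but it pays once R² exceeds about 0.003. The primary conclusion is not affected.

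The caution about the Visit 1 prescribed dose does not depend on any assumed correlation. It follows from reading SAP 7.1 beside footnote d of the Schedule of Activities.

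**What to change.** Amend SAP 8.2.2 item 5:
- At Weeks 24 and 48, analyse daily insulin dose by ANCOVA with treatment as fixed effect. For IU, use baseline HbA1c and baseline body weight as covariates. For IU/kg, baseline HbA1c may suffice.
- Report the LS mean difference between arms with its 95% CI and p-value, on both scales.
- Keep the descriptive table by visit.
- State that the dose prescribed at Visit 1 is not used as a baseline covariate or to compute change from baseline, because it reflects the assigned regimen. Make SAP 7.1 consistent with this.

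The cost is a few lines of SAP text and a standard model, with no new data. Report how many patients are left out for a missing baseline covariate.

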8.3. Exploratory Analyses

All exploratory endpoints will be listed for each subject at each planned visit.

8.3.1. Adherence and Insulin Treatment Pattern

For these measurements which are the insulin treatment pattern for insulin discontinuation, switch, intensification or reduction in frequency, summary statistics will be provided, and comparison will be performed by appropriate general test (Fisher's exact test). Proportion of patients who experience insulin discontinuation, switch, intensification or reduction in frequency during 48 weeks and P value should be in summary statistics.

8.3.2. Resource Utilization

Utilization data will be summarized descriptively by category across arms (for example, surgery, hospitalization type, reason for hospitalization, T2DM-related and hospitalization days) for a treatment arm, including a frequency table with tabular statistics. Fisher's exact test for differences in proportions between treatment arms will be performed.

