5.4. Scientific Rationale for Study Design

Given the results of the previous IOQI randomized clinical trial, this pragmatic study is designed to demonstrate that the results drawn from the randomized clinical trial can be applied in more generalizable populations and real world settings.

According to the scientific questions raised, instead of a randomized clinical trial (RCT) or a prospective observational study, a PCT is selected because the study aims to compare effectiveness in real world settings with minimal intervention while randomization is required to remove selection bias and other confounding factors between arms.

Two arms including basal insulin analog, and insulin analog mid mixture will be compared in a Chinese general T2DM population. The following considerations have been incorporated into study design to ensure a robust study that represents real world situations:

- Restriction on inclusion and exclusion criteria for patients in this study is minimal compared with a typical RCT. Patients enrolled will represent a general T2DM population with uncontrolled HbA1c levels under OAM.
- There is also no restriction on insulin titration algorithm and OAM use. Also there is no restriction on switching or augmenting the initial insulin treatment. Physicians can pursue their general practice governed by local guideline.
- The schedule of visits is aimed to reflect real-world practice. In general, the frequency of visits to physician offices after insulin initiation is weekly or biweekly in a real world setting for dose titration and adjustment (CDS 2013). Therefore, the potential intervention brought by the scheduled monthly or every 3 month visits could be considered minimal.
- The duration of this study is 48 weeks which is relatively longer than a typical RCT with 24 or 26 weeks comparing 2 insulin regimens by measuring HbA1c. So adequate information from real world settings could be observed and collected.
- In China, the community based primary care health system is not well developed, and most of the patients go to see the endocrinologists to start insulin treatment instead of general practitioners. Therefore in this study, no community based clinical center will be selected as study sites.

In summary, the study design presented is intended to provide a better understanding of the real-world feasibility and performance of initiating insulin treatment with insulin analog mixtures.

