7.8.4. Patient Follow-Up in Pragmatic Trials

Patient follow-up is dictated only by usual care, no additional visit is required by the protocol.

8. Discontinuation Criteria

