9.9.3. Healthcare Resource Utilization

Medical resource utilization data, associated with medical encounters, will be collected in the CRF by the investigator and study-site personnel for all participants throughout the study. Protocol-mandated procedures, tests, and encounters are excluded.

Healthcare resource utilization will be examined as all-cause and T2DM-related, and categorized as inpatient, outpatient, and ER utilizations:

- Inpatient hospital utilization will be identified using medical encounters where the place of service is an inpatient hospital facility.
- Outpatient utilization will be identified using medical encounters where the place of service is outpatient facility.
- Emergency room utilization will be identified using medical encounters where the place of service is an ER. Emergency room claims that have the same service date as a hospitalization will not be counted as an ER visit. Emergency room visits adjacent to a hospitalization will be considered a hospitalization and will not be counted as an ER visit.

The data collected may be used to conduct exploratory economic analyses and will include:

- number and duration of medical care encounters, including surgeries, and other selected procedures (inpatient and outpatient)
- reason and duration of hospitalization (total days length of stay, including duration by wards; for example, intensive care unit)
- number and character of diagnostic and therapeutic tests and procedures

10. Statistical Considerations

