10.3.6.1.2. Resource Utilization

Utilization data will be summarized descriptively by category across arms (for example, surgery, and hospitalization days) for a treatment arm, including a frequency table with tabular statistics. Tests for differences in proportions between treatment arms will be performed.

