9. To compare time to insulin treatment change between insulin analog mid mixture BID and basal insulin analog QD treatments	
9. Time to insulin treatment change: Defined as time to any of: insulin treatment discontinuation, switch, intensification or reduction in frequency
 
Discontinuation: Defined as stopping insulin treatment for 30 days or more.
 
Switch: Defined as stop the initial insulin therapy and started another insulin therapy of different class.
 
Intensification: Defined as any of the following: adding meal time insulin in basal insulin analog QD group; changing from BID to TID in insulin analog mid mixture BID group
 
Reduction in frequency: Defined as any of the following: changing from BID to QD; changing from TID to BID or QD

10. To compare the proportion of patients who achieve the HbA1c <7% without switching and discontinuing study insulin, and without using rescue therapy between insulin analog mid mixture BID and basal insulin analog QD treatments	10. Proportion of patients who achieve the HbA1c <7% without switching and discontinuing study insulin, and without using rescue therapy
11. To compare the patients-reported self-efficacy related to insulin therapy as assessed using SEITQ between insulin analog mid mixture BID and basal insulin analog QD treatments	11. The change in SEITQ score form baseline at 48 weeks

Tertiary/Exploratory	

12. To compare the insulin treatment pattern for
 
 • discontinuation • switch • intensification • reduction in frequency 
between insulin analog mid mixture BID and basal insulin analog QD treatments
	
12. Time to insulin discontinuation, switch, intensification or reduction in frequency
 
Proportion of patients who experience insulin discontinuation, switch, intensification or reduction in frequency during 48 weeks

13. To compare healthcare resource utilization (all-cause and T2DM-related; inpatient, outpatient and ER) between insulin analog mid mixture BID and basal insulin analog QD treatments
	
13. Healthcare resource utilization (all-cause and T2DM-related; inpatient, outpatient and ER) during 48 weeks

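### Healthcare use (exploratory endpoint 13) is tested only as an undefined proportion, with no comparison of visit counts or rates, and the rule on which visits count is unclear

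*SAP*

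**What the plan says.** Endpoint 13 is exploratory: "Healthcare resource utilization (all-cause and T2DM-related; inpatient, outpatient and ER) during 48 weeks" (SAP section 3; the same in Protocol Table IOQR.2).

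- **Analysis.** Protocol 10.3.6.1.2 says "Tests for differences in proportions between treatment arms will be performed". SAP 8.3.2 makes this specific: "Fisher's exact test for differences in proportions between treatment arms will be performed". The rest of SAP 8.3.2 is descriptive: "Utilization data will be summarized descriptively by category across arms", with hospitalization days among the examples. Neither section says what the proportion is of.
- **Data.** Protocol 9.9.3 lists the number and duration of encounters among the data that will be available.
- **Expected visit frequency.** Protocol 5.4 says that "the frequency of visits to physician offices after insulin initiation is weekly or biweekly in a real world setting". It ties this to dose titration and gives no duration.
- **Which visits count.** Protocol 9.9.3: "Protocol-mandated procedures, tests, and encounters are excluded". Protocol 7.8.4: "Patient follow-up is dictated only by usual care, no additional visit is required by the protocol". The Schedule of Activities (Protocol section 2) sets five post-baseline visits, at Weeks 4, 12, 24, 36 and 48.

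**The concern.** Two things looked wrong.

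First, the named test does not use the information collected. A test of any use against none discards the number of visits. Where most patients have at least one visit, little is left to compare. Outpatient use is the category most exposed to this, because patients starting insulin are seen often.

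Second, the counting rule is unclear. If no visit is protocol-required, nothing is excluded; if the scheduled visits are protocol-mandated, up to five per patient are. No section says how to treat a scheduled visit that is also routine care.

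At stake is whether the outpatient comparison can show a difference in visit burden between a once-daily and a twice-daily starter regimen, and whether the utilization tables mean the same thing at every site.

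**Working it through.** **The plan's figures.** No figure is given for healthcare use. The only sizing is for HbA1c: 332 evaluable per arm with 20% dropout, and 332 / (1 − 0.20) = 415, which reproduces the stated number randomized. I use 415 per arm and two-sided alpha 0.05.

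**Assumptions (not in the documents).** The proportion is patients with at least one outpatient visit. Visits are Poisson (dispersion k = 0) or negative binomial (k up to 1). One arm has 25% more visits than the other. All patients are followed for 48 weeks.

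**Mean visits in the lower arm.** Protocol 5.4 gives a frequency but no duration, so I span the range with biweekly visits:

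- for 48 weeks: 24 (19 if the five scheduled visits are removed)
- for 24 weeks: 12
- for 12 weeks: 6 (4 if the Week 4 and Week 12 visits are removed)
- for 4 weeks: 2 (1 if the Week 4 visit is removed)

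**Formulas.** For mean m, the share with any visit is 1 − exp(−m) if k = 0, otherwise 1 − (1 + km)^(−1/k). Fisher power is the exact sum over both binomial distributions. For the count model, SE(log rate ratio) = sqrt[(1/m1 + 1/m2 + 2k)/n], and power = Φ(ln 1.25/SE − 1.96), with ln 1.25 = 0.2231.

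**Worked case, m = 6 v 7.5, k = 0.5.** The shares are 1 − 4^(−2) = 93.75% and 1 − 4.75^(−2) = 95.57%, and Fisher power is 17.3%. SE = sqrt[(0.1667 + 0.1333 + 1)/415] = 0.0560, so count-model power is Φ(3.99 − 1.96) = 97.9%.

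| Mean, lower arm | Any visit, k = 0 | Any visit, k = 1 | Fisher power %, k = 0 / 0.25 / 0.5 / 1 | Count-model power %, same k |
|---|---|---|---|---|
| 1 | 63.2 v 71.3% | 50.0 v 55.6% | 68.1 / 55.1 / 46.4 / 32.8 | 92.3 / 85.0 / 77.5 / 64.5 |
| 4 | 98.2 v 99.3% | 80.0 v 83.3% | 21.3 / 28.5 / 26.5 / 21.1 | >99 / 99.7 / 96.5 / 82.7 |
| 6 | 99.8 v 99.9% | 85.7 v 88.2% | 0.1 / 14.2 / 17.3 / 16.4 | >99 / 99.9 / 97.9 / 85.0 |
| 12 | 100 v 100% | 92.3 v 93.8% | 0.0 / 0.3 / 6.7 / 10.3 | >99 / >99 / 98.9 / 87.3 |
| 24 | 100 v 100% | 96.0 v 96.8% | 0.0 / 0.0 / 0.9 / 6.5 | >99 / >99 / 99.2 / 88.4 |

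**Sensitivity.**

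- With 332 per arm, Fisher power is 0-14% at means 6 to 24, 15-22% at mean 4 and 27-58% at mean 1; the count model has 55-100%.
- If one arm instead has 25% fewer visits, at 415 per arm, Fisher power is 38-67% at mean 4 and 51-85% at mean 1, against 95% or more and 80-97% for the count model. At a mean of 24 it is 0-11% against 98% or more.

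The count model is ahead in every setting. The ceiling is not present in every setting: at a mean of 1 only 50-63% of the lower arm has a visit.

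**The case against.** **A ceiling is not documented.** A reader might infer from Protocol 5.4 that nearly every patient will have an outpatient visit, so that the test will show no difference whatever the truth. The documents do not support this. The visit frequency is a general statement tied to titration, with no duration and no 48-week count. Until the counting rule is settled, the share of patients with a countable visit is unknown as well. This objection stands, and the ceiling is stated here only as a condition.

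**Other clauses could cover counts.** SAP section 8 has a default: "Unless specified otherwise, a two-sample t-test will be used for continuous measurements and Fisher's exact test will be used for categorical measurements". The protocol synopsis promises an appropriate general test for resource use. This is a weak rescue. The default yields to specific wording, SAP 8.3.2 names Fisher's test, and SAP 8.3.3 and 8.3.4 name the t-test where it is wanted. A t-test on raw counts would also ignore unequal follow-up. It is true that reading the proportion as patients with any use is an inference, since the SAP leaves it undefined.

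**The visit rules can be partly reconciled.** Protocol 7.8.4 says no additional visit is required, and 5.4 describes the scheduled visits as sparser than usual care, so they can be read as part of routine follow-up. That leaves an ambiguity rather than a flat contradiction. A reader might also infer that inconsistent counting biases the comparison. Nothing in the documents shows this: the exclusion is not arm-specific and patients are randomized, so the expected effect is noise or dilution.

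**The consequence is limited.** The endpoint is exploratory, SAP section 8 allows further exploratory analyses, and a proportion is a reasonable measure for any hospitalization or any ER visit. All of this stands.

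**Conclusion.** The concern holds in a limited form. The test named for endpoint 13 is on an undefined proportion, and no comparison of encounter counts or rates is specified although the data are collected. Read as any outpatient visit, that test has about 0-17% power at means of 6 to 24 visits, 21-29% at a mean of 4 and 33-68% at a mean of 1, against about 65-100% for a count model. These figures rest on an assumed 25% difference in visits, dispersion 0 to 1, 415 per arm with complete follow-up, and counts that follow the assumed distribution. Only part of the loss is a ceiling effect; the rest comes from reducing counts to yes or no.

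Separately, and without any assumption, Protocol 9.9.3, 7.8.4 and section 2 do not settle whether a scheduled visit that is also routine care counts. The power argument covers outpatient use only. This is a cheap improvement to an exploratory analysis.

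**What to change.** **SAP 8.3.2.** Define the proportion as patients with at least one encounter in the category. Keep Fisher's test for any hospitalization and any ER visit. Compare outpatient visits per patient-year with a negative-binomial model, treatment as fixed effect and log follow-up time as offset, as SAP 8.4.4 does for hypoglycemia, and report the rate ratio with its 95% CI.

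**Protocol 9.9.3.** Reconcile it with 7.8.4 and the section 2 schedule by stating one rule for every site on whether a scheduled visit that is also routine care counts. One workable rule is to count every encounter except a visit made only for study data collection, flagged in the CRF.

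**Cost.** A few sentences of SAP wording, one sentence in the protocol, slightly more analysis work and one visit flag in the CRF. Encounter numbers are already collected. The flag should be in place prospectively, because uneven counting across sites may be hard to correct afterwards.
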